8.1 Participants

Approximately **38 habitual** soft toric contact lens wearers will be enrolled. Each subject will be required to attend up to **six** scheduled study visits over a period of approximately two months.

Each subject will be given a unique ID number. Additionally, all subjects must meet the study inclusion and exclusion criteria listed below.

Inclusion criteria

A person is eligible for inclusion in the study if he/she:

- A person is eligible for inclusion in the study if he/she:
- Is between 18 and 40 years of age (inclusive)
- Has had a self-reported visual exam in the last two years
- Is an adapted soft contact lens wearer
- Is not a habitual wearer of either study lens
- Has a contact lens spherical prescription between +4.00 to - 10.00 (inclusive) Best corrected visual acuity of 20/30 or better in either eye
- Have contact lens prescription of no less than -0.75D of astigmatism and no more than -2.25 D in both eyes.
- Can achieve best corrected spectacle distance visual acuity of 20/25 (0.10 logMAR) or better in each eye.
- Can achieve a distance visual acuity of 20/30 (0.18 logMAR) or better in each eye with the study contact lenses.
- Has clear corneas and no active ocular disease
- Has read, understood and signed the information consent letter.
- Patient contact lens refraction should fit within the available parameters of the study lenses.
- Is willing to comply with the wear schedule (at least 5 days per week, > 8 hours/day assuming there are no contraindications for doing so).
- Is willing to comply with the visit schedule

Exclusion Criteria

A person will be excluded from the study if he/she:

- A person was excluded from the study if he/she:
- Has a CL prescription outside the range of the available parameters of the study lenses.
- Has a spectacle cylinder less than -0.75D or more than -2.50 D of cylinder in either eye.
- Has a history of not achieving comfortable CL wear (5 days per week; > 8 hours/day)
- Has contact lens best corrected distance vision worse than 20/25 (0.10 logMAR) in either eye.
- Presence of clinically significant (grade 2-4) anterior segment abnormalities
- Presence of ocular or systemic disease or need of medications which might interfere with contact lens wear.
- Slit lamp findings that would contraindicate contact lens wear such as:
 - Pathological dry eye or associated findings
 - Pterygium, pinguecula, or corneal scars within the visual axis
 - Neovascularization > 0.75 mm in from of the limbus

- Giant papillary conjunctivitis (GCP) worse than grade 1
- Anterior uveitis or iritis (past or present)
- Seborrheic eczema, Seborrheic conjunctivitis
- History of corneal ulcers or fungal infections
- Poor personal hygiene
- Has a known history of corneal hypoesthesia (reduced corneal sensitivity)
- Has aphakia, keratoconus or a highly irregular cornea.
- Has Presbyopia or has dependence on spectacles for near work over the contact lenses.
- Has undergone corneal refractive surgery.
- Is participating in any other type of eye related clinical or research study.

8.2 Study Materials

8.2.1 Contact lens

All subjects will be trial fitted and, if suitable, dispensed the Avaira Vitality™ toric and Miru 1month toric lenses. The study toric lenses and solutions will be provided by the Sponsor. Details of the contact lenses are shown in Table 1.

Table1: Study lenses

	Avaira Vitality™ toric	Miru 1month Menicon toric
Manufacturer	CooperVision	Menicon
Material	fanfilcon A	asmofilcon A
WC %	55%	40%
Base Curve	8.5 mm	8.6 mm
Lens Diameter	14.5 mm	14.0 mm
Lens Powers Sphere	+4.00 to – 10.00	+4.00 to -10.00
Lens Power Cylinder	-0.75, -1.25, - 1.75, -2.25	-0.75, -1.25, - 1.75, -2.25
Axis cylinder	10 degrees to 180 degrees in 10 degree steps	10 degrees to 180 degrees in 10 degree steps
Wearing schedule	Daily wear	Daily wear

8.2.2 Contact Lens care

OPTI-FREE® PureMoist® multipurpose disinfecting solution and lens cases (Alcon, Fort Worth, TX) will be provided to all subjects for care and maintenance of the contact lenses during the study.

8.2.3 Storage of Study Medications/Treatments

There are no unapproved investigational products used in this study requiring special storage accommodations.

8.2.4 Clinical Supply Inventory

There are no unapproved investigational products used in this study requiring special inventory requirements.

8.2.5 Disposal of Consumables

This study dispenses consumables (lenses) to participants for use during the study. Study lenses worn for the full 1-month of daily wear by participants will be collected at the last visit and destroyed.

8.2.6 Masking and Control of Study Materials

The study contact lenses will be **masked to BOTH, the subject and investigator**. Study lenses will be transferred, by an assistant, out of their packaging to unmarked new contact lens cases filled with unpreserved sterile saline just prior to dispensing to maintain subject masking of the study lenses.

8.2.7 Ordering and Accountability of Study Materials

The study lenses and solutions will be provided by the sponsor. If additional lenses are required, the study sponsor will re-supply the investigator as requested.

8.3 Visit Schedule and Procedures

8.3.1 Visit 1: Baseline and fitting visit (screening and enrollment)

The following evaluations will be performed to assess eligibility according to the Inclusion and Exclusion Criteria at the baseline visit only:

- The subjects should attend the first visit wearing their habitual contact lenses and having worn them that day for at least 2 hours prior to the visit. If they are not wearing their lenses, please reschedule the visit.
- The subject will be required to read and sign an Informed Consent Form prior to enrolment. When the subject has signed the consent form, the subject will be considered to be enrolled on to the study.
- The person explaining the consent and Investigator should also sign the consent form. Provide the subject with a copy and keep the original in the subject's paper chart or scan into the subject's electronic medical record (EMR) file.
- The subject is assigned with a Subject ID number. Subjects must be enrolled sequentially.

- Full anterior segment ocular health will be established.

-

Visit 1a: Baseline habitual lenses

- Details of current lens:
 - Brand (no more than three subjects in any study lens brand allowed)
 - Power(s)
 - Replacement schedule (daily, 2-week, monthly)
 - Lens age (days).

The following baseline measurements and assessments will be recorded:

- [REDACTED]
- [REDACTED]
- [REDACTED]
 - [REDACTED]
 - [REDACTED]
 - [REDACTED]
- Habitual lens subjective binocular ratings
 - [REDACTED]
 - [REDACTED]
 - Handling (insertion & removal, 0-10 scale)
 - [REDACTED]
 - [REDACTED]
 - [REDACTED]
 - [REDACTED]
- [REDACTED]
 - [REDACTED]
 - [REDACTED]
 - [REDACTED]
 - [REDACTED]
 - [REDACTED]
- [REDACTED]
 - [REDACTED]
 - [REDACTED]
- [REDACTED]
 - [REDACTED]
 - [REDACTED]

- [REDACTED]
- [REDACTED]
- [REDACTED]
- [REDACTED]
- [REDACTED]
- [REDACTED]
- [REDACTED]
- [REDACTED]
- [REDACTED]
 - [REDACTED]
 - [REDACTED]
- [REDACTED]
 - [REDACTED]
- [REDACTED]
 - [REDACTED]
 - [REDACTED]
- [REDACTED]
- Complete the eligibility checklist.
- If at this point the subject is found to be ineligible, then complete an Exit form and exit the subject from the study.

Visit 1 b: Trial fitting visit

If eligible, complete the Enrolment Log and identify the test lens [REDACTED]. The subjects will undergo a trial fit in both eyes with both study lenses (e.g., Avaira Vitality Toric and Miru 1month Menicon toric, according to manufacturer’s fitting guides) to ensure optimization of the lens parameters needed to provide the best distance visual acuity. Re-order final lens if appropriate. If the lenses are not suitable to be dispensed, then the subject will be discontinued and an Exit form will be completed.

8.3.2 Visit 2: Dispense pair 1

- Data is only collected on the final pair of study lenses dispensed after the power has been assessed and if needed corrected.

- Record the parameters of the lenses, [REDACTED] on the Dispensing CRF [REDACTED]
- [REDACTED]
 - [REDACTED]
 - [REDACTED]
 - [REDACTED]
 - [REDACTED]
 - [REDACTED]
 - [REDACTED]
 - [REDACTED]
- [REDACTED]
 - [REDACTED]
 - [REDACTED]
- [REDACTED]
 - [REDACTED]
 - [REDACTED]
 - [REDACTED]
 - [REDACTED]
 - [REDACTED]
 - [REDACTED]
 - [REDACTED]
 - [REDACTED]
 - [REDACTED]
- [REDACTED]
 - [REDACTED]
- Lost or damaged study lenses may be replaced. Note which lens was replaced, date of replacement and reason for replacement on the Lens Replacement Log, [REDACTED]
- The subject will be instructed to wear the lenses on a daily wear basis, (at least 40 hours per week), until the 2-weeks follow-up appointment, unless they experience a problem which warrants lens removal.
- The Investigator or a clinical assistant will review instructions and warnings for lens wear, when to remove lenses, and other important issues with the participant.

- Participants, who appear unable or unwilling to follow instructions to a degree that, in the Investigator's opinion, jeopardises the participant's wellbeing or the validity of the study, will be discontinued. The reason for discontinuation will be documented.
- The subject will be discharged and asked to return for a follow-up visit (V2) after 1-month.

8.3.3 Visit 3: 2-week follow-up pair 1

The 2-week follow-up visit will be scheduled one month (**14 ± 2 days**) from the initial lens dispensing date. The subject should wear the lenses for a minimum of 2 hours prior to the appointment. If the subject attends without lenses or with less than 2 hours of lens wear on that day and they are not having any problems with their lenses, the visit should be rescheduled, if possible, within the visit window.

- The following clinical test variables will be recorded on the Follow-Up Visit CRF:

- [Redacted]
- Subjective Assessments
 - [Redacted]
 - Handling (insertion & removal, 0-10 scale)
 - [Redacted]
 - [Redacted]
 - [Redacted]
 - [Redacted]
 - [Redacted]
 - [Redacted]
 - [Redacted]
 - [Redacted]
 - [Redacted]
 - [Redacted]
 - [Redacted]
 - [Redacted]
 - [Redacted]
 - [Redacted]
 - [Redacted]
 - [Redacted]
 - [Redacted]

- [REDACTED]
 - | [REDACTED]
 - | [REDACTED]
- [REDACTED]
 - [REDACTED]
 - [REDACTED]
- [REDACTED]
 - | [REDACTED]
 - | [REDACTED]
 - | [REDACTED]
 - [REDACTED]
 - [REDACTED]
 - [REDACTED]
 - [REDACTED]
 - [REDACTED]
 - [REDACTED]
 - [REDACTED]

[figure not shown]
8.3.4 Visit 4: 1-month follow-up pair 1/dispenses pair 2

The 1-month follow-up visit will be scheduled one month (**28 + 2 days**) from the initial lens dispensing date. The subject should wear the lenses for a minimum of 2 hours prior to the appointment. If the subject attends without lenses or with less than 2 hours of lens wear on that day and they are not having any problems with their lenses, the visit should be rescheduled, if possible, within the visit window.

Visit 4a: Lens evaluation pair 1

- The following clinical test variables will be recorded on the Follow-Up Visit CRF:

- [REDACTED]
 - [REDACTED]
 - [REDACTED]
 - [REDACTED]
 - [REDACTED]
- Subjective Assessments
 - [REDACTED]
 - [REDACTED]
 - Handling (insertion & removal, 0-10 scale)
 - [REDACTED]
 - [REDACTED]

Visit 4b: Dispense pair 2

The study subjects will undergo a trial fit in each eye with the second pair of study lenses.

- The performance of the second pair of study lenses should be assessed after 10-15 minutes settling time and the same variables as those collected on *visit 2* (section 8.3.2) will be assessed.

8.3.5 Visit 5: 2-week follow-up pair 2

The 2-week follow-up visit will be scheduled one month (14 + 2 days) from the initial lens dispensing date. The subject should wear the lenses for a minimum of 2 hours prior to the appointment. If the subject attends without lenses or with less than 2 hours of lens wear on that day and they are not having any problems with their lenses, the visit should be rescheduled, if possible, within the visit window. The same variables as those collected on section 8.3.3 will be assessed at this visit.

8.3.6 Visit 6: 1-month follow-up pair 2 / Exit

Visit 6a: Lens evaluation pair 2

The 1-month follow-up visit for pair 2 will be scheduled one month (28 ± 2 days) from the initial lens dispensing date for pair 2. The subject should wear the lenses for a minimum of 2 hours prior to the appointment. If the subject attends without lenses or with less than 2 hours of lens wear on that day and they are not having any problems with their lenses, the visit should be rescheduled, if possible, within the visit window. The same variables as those collected on section 8.3.4 will be assessed at this visit.

Visit 6b: Study exit

- The Study Exit Form must be completed when a subject exits the study. This will occur either at study completion, i.e., at Visit 3, or if the subject is discontinued from the study at another time. If there are records entered into the clinic's own patient chart system the exit date should be recorded on these source documents.
- A Study Exit Form must be completed for all subjects who have taken a study ID number. Post-study follow-up visits will be scheduled if the Investigator judges this is necessary.
- At the study Exit Visit the following measurements are taken:

○

[REDACTED]

■

[REDACTED]

○

[REDACTED]

- Post-study follow-up requirement (Y/N). If yes, the reason and date of the follow-visit must also be recorded.
- If the subject is being exited due to discontinuation, further details need to be recorded on the exit form.

9 Adverse Event Reporting

9.1 Adverse Response Definitions

Adverse Event (AE): An AE refers to any untoward medical occurrence (sign, symptom or disease) in a trial subject that does not necessarily have a causal relationship with the study device. AEs may be classified as ‘unanticipated adverse device effects,’ ‘serious AEs,’ ‘significant AEs,’ or ‘non-significant AEs,’ as defined below.

Classification	Definition
Serious Adverse Event	Those events that are life-threatening, or result in permanent impairment of a body function, or permanent damage to a body structure or necessitate medical (therapeutic) or surgical intervention to preclude permanent impairment of a body function or permanent damage to a body structure.
Unanticipated Adverse Device Effect	Adverse events in a clinical trial that were not previously identified in the protocol in terms of nature, severity, or degree of incidence. An Unanticipated Serious Adverse Device Effect is an unanticipated adverse event that is serious in nature and caused by or associated with the device and is considered reportable.
Significant Adverse Event	Those non-serious adverse events that occur with contact lens usage that are not sight-threatening but are usually symptomatic and may warrant therapeutic management and /or temporary or permanent discontinuation of contact lens wear.
Non-Significant Adverse Events	Those less severe non-serious adverse events that occur with contact lens usage that are not sight-threatening, may or may not be symptomatic and may warrant palliative management, such as ocular lubricants or temporary interruption of contact lens wear.

AE classification, coding (for reporting to the sponsor) and examples are provided in the following table of Contact Lens Adverse Event Classification and Reporting:

Code	Condition	Potential AE Classification	Reporting
01	Presumed infectious corneal ulcer	SERIOUS	Notify sponsor as soon as possible, within 24 hrs; IRB
02	Permanent loss of ≥ 2 lines of best spectacle corrected visual acuity (BSCVA)	SERIOUS	

03	Corneal injury that results in permanent opacification within central cornea (6mm)	SERIOUS	reporting as per requirements
04	Neovascularization within the central 6mm of cornea	SERIOUS	
05	Uveitis or Iritis	SERIOUS	
06	Endophthalmitis	SERIOUS	
07	Hyphema	SERIOUS	
08	Hypopyon	SERIOUS	
09	Persistent epithelial defect	SERIOUS	
00	Other serious event	SERIOUS	
11	Peripheral non-infectious ulcer (outside central 6mm)	SIGNIFICANT	Notify sponsor as soon as possible, within 5 working days; IRB reporting as per requirements
12	Symptomatic corneal infiltrative events	SIGNIFICANT	
13	Superior epithelial arcuate lesions (SEALs) involving epithelial split	SIGNIFICANT	
14	Any temporary loss of ≥ 2 lines BSCVA for ≥ 2 wks	SIGNIFICANT	
15	Corneal staining \geq dense coalescent staining up to 2mm in diameter (i.e. moderate staining)	SIGNIFICANT	
16	Corneal neovascularization ≥ 1.0 mm to 1.5mm vessel penetration (if 2 Grade change from baseline)	SIGNIFICANT	
17	Any sign and/or symptom for which subject is administered therapeutic treatment or which necessitates discontinuation of lens wear for ≥ 2 weeks	SIGNIFICANT	
10	Other significant event	SIGNIFICANT	
21	Conjunctivitis: bacterial, viral, allergic	NON-SIGNIFICANT	
22	Papillary conjunctivitis if \geq mild scattered papillae/follicles approximately 1mm in diameter (if 2 Grade change from baseline)	NON-SIGNIFICANT	
25	Asymptomatic corneal infiltrative events	NON-SIGNIFICANT	
26	Localized allergic reaction	NON-SIGNIFICANT	
27	Contact dermatitis	NON-SIGNIFICANT	
28	Any sign and/or symptom for which temporary lens discontinuation for > 1 day is recommended	NON-SIGNIFICANT	
20	Other non-significant sign and/or symptom	NON-SIGNIFICANT	

Normal or adaptive symptoms

Transient symptoms such as end-of-day dryness, lens awareness, itching or burning or other discomfort may occur with contact lens wear and may occasionally reduce wearing time. **These**

are not reported as adverse events unless they are unexpected in nature, severity or rate of occurrence.

9.2 Procedures for Adverse Events

Treatment of an adverse event will depend on its nature and severity. Based on the clinical judgment of the investigator the subject may be referred to an ophthalmologist for treatment. The investigator will attempt to determine whether the reaction is related to the test device or a result of other factors.

An Adverse Event Form will be completed for each adverse event. If both eyes are involved, a separate Adverse Event Form will be completed for each eye. Whenever possible, the adverse event will be photo-documented.

Expenses incurred for medical treatment as part of study participation will be paid by the sponsor (bills and prescription receipts kept). The subject must be followed until resolution and a written report completed indicating the subsequent treatment and resolution of the condition.

9.3 Discontinuation from the Study

All discontinuations will be fully documented on the appropriate CRF Exit and Adverse Event forms as needed. Participants will be followed until resolution (in most instances) and are free of the ophthalmic insert related complications or other ocular pathology. When possible study lenses involved in an Adverse Event will be returned to the sponsor in a new tightly sealed contact lens case, and labeled with the subject identification and stored in Unisol non-preserved saline.

9.4 Reporting Adverse Events

All potential **Serious and Unanticipated Adverse Device Effects** that are related or possibly related to subject participation in the investigation will be reported to the Principal Investigator and the sponsor within 24 hours of the investigator becoming aware of the event. The Principal Investigator will report the event to the EC/IRB as soon as possible (by fax, mail/delivery, phone, or email), but within 10 business days of becoming aware of the problem. *All fatal or life threatening events will be reported immediately to the IRB.*

Significant and Non-Significant Adverse Events will be reported to the sponsor as soon as possible, but no later than 5 working days after the occurrence. [REDACTED]

[REDACTED]

[figure not shown]
10 Statistical Analysis and Sample Size

10.1 Statistical analysis

Summary statistics will be produced (e.g., mean, standard deviation). Differences between lenses will be compared using Paired t-tests. Paired t-tests /analysis of variance for normal (interval/continuous) data, Wilcoxon's signed ranks test for non-normal (ordinal) data, chi-squares test for nominal data. A Binomial test will be used to evaluate lens preference questions. All participants who were evaluated will be used in the analysis. In the event of missing data, individual data points will be excluded in the analysis and not extrapolated from the collected data.

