3.1 Study Hypothesis

- Null hypothesis (Ho): There is no difference between the Avaira Vitality™ toric and Miru 1month toric Menicon lenses in subjective lens handling ratings.
- Alternative hypothesis (H1): There is a difference between the Avaira Vitality™ toric and Miru 1month toric Menicon lenses in subjective lens handling ratings.

4 Study Design

This is a 38-subject, prospective, randomized, double masked, (investigator and participant), bilateral, 1 month cross-over study comparing the handling characteristics, (insertion & removal), of asofilcon A toric lenses against fanfilcon A silicone hydrogel toric lenses (table 1). It is anticipated that this study will involve up to 6 scheduled visits: At the first visit, (V1), subject's habitual toric lenses will be evaluated and then re-fitted with both study lenses [REDACTED]. At the second visit, (V2), the first pair of study lenses, (e.g., asofilcon A or fanfilcon A toric lenses), will be dispensed. After 2 -weeks of daily wear, subjects will return for a third evaluation, (V3), and a 4-week visit will be scheduled. At the 4-week visit, (V4), pair 1 will be evaluated and then pair 2 dispensed. Next, a 2-week, (V5), and 4-week visits, (V6) will be scheduled. At visit 6, subjects will exit the study. [REDACTED]

5 Investigational Sites

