10.2 Sample size

Figure 1 shows the sample size determination for a paired t-test, ($\alpha=0.05$), in order to detect a difference in mean subjective handling scores between lenses. Assuming a standard deviation of 1.2, a sample size of about 33 completed subjects provides 90% power to detect a difference in subjective handling ratings of 0.7 points on a 0 - 10 scale. In order to account for potential subject dropouts or AEs, 10%-15% should be added to the sample size. Therefore, 38 subjects should be enrolled with the aim to complete 33.

11 Data Quality Assurance

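### The cross-over analysis has no period term; if handling ratings drift between months, the paired test loses some power, which a period term recovers at almost no cost

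*Combined protocol and SAP*

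**What the plan says.** Section 4 describes a "prospective, randomized, double masked, (investigator and participant), bilateral, 1 month cross-over study". At Visit 4, "pair 1 will be evaluated and then pair 2 dispensed", so each subject contributes one month on each lens and only the randomised order separates lens from period.

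Section 10.1 states that "Differences between lenses will be compared using Paired t-tests". It then lists "Paired t-tests /analysis of variance for normal (interval/continuous) data", with Wilcoxon signed ranks for non-normal ordinal data. No factors are given for the analysis of variance, and neither period nor sequence is mentioned. No text is blacked out in that section.

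Section 10.2 sizes the trial on a plain paired t-test: "Assuming a standard deviation of 1.2, a sample size of about 33 completed subjects provides 90% power" to detect 0.7 points on the 0 to 10 handling scale, and "38 subjects should be enrolled with the aim to complete 33".

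**The concern.** Suppose ratings move by *p* points from month 1 to month 2 for either lens, through practice or a change in how subjects use the scale. A subject who wears lens A first has an A-minus-B difference lowered by *p*; a subject who wears B first has it raised by *p*. A one-sample test on the pooled differences treats this systematic gap between sequences as random noise. Two things follow:

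- the standard error grows, so power falls and the confidence interval widens;
- if the sequences finish unequal, the mean difference is biased by *p* times the imbalance divided by *n*.

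The primary outcome is ease of insertion and removal, and Section 8.1 excludes habitual wearers of either study lens, so some shift is plausible. The sample size leaves no reserve to absorb it: 33 is the smallest number of completers that reaches 90% power on the plan's own inputs.

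**Working it through.** **Inputs.** From Section 10.2: lens difference 0.7, SD 1.2, 33 completers, 38 enrolled, alpha 0.05. The test is taken as two-sided because the alternative hypothesis in Section 3.1 has no direction. Assumptions: 1.2 is the SD of within-subject lens differences and contains no period variance (Section 10.2 does not say); *p* is not in the documents, so 0 to 0.7 is shown.

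**1. The plan's own figure.** Noncentrality = 0.7 × √33 / 1.2 = 3.351 on 32 df, which gives power 90.1%. With 32 completers it is 89.2%. The stated 90% at 33 reproduces.

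**2. Effect of a shift on the paired test.** The differences are 0.7 − *p* in one sequence and 0.7 + *p* in the other, plus normal error with SD 1.2. For a 17/16 split and *p* = 0.5:

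- expected sample variance = 1.2² + 0.5² × 4 × 17 × 16 / (33 × 32) = 1.44 + 0.258 = 1.698, so the SD is 1.30 instead of 1.2;
- bias = 0.5 × 1 / 33 = 0.015 points.

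**3. Effect with a period term.** The estimate is the mean of the two sequence means, with pooled within-sequence variance on 31 df. SE = (1.2 / 2) × √(1/17 + 1/16) = 0.209; noncentrality = 0.7 / 0.209 = 3.349; power 90.0% whatever *p* is.

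**4. Simulated power at 17/16** (100,000 trials per cell). The two paired-test figures are for bias against and with the lens effect.

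| Shift *p* | Paired t | With period term | Paired t, type I error |
|---|---|---|---|
| 0 | 90% | 90% | 5.0% |
| 0.3 | 88% / 90% | 90% | 4.4% |
| 0.5 | 85% / 88% | 90% | 3.5% |
| 0.7 | 81% / 86% | 90% | 2.5% |

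At *p* = 0.5 the mean half-width of the 95% CI is 0.46 unadjusted and 0.42 adjusted. Wilcoxon signed ranks behaves similarly: 83% / 86% at *p* = 0.5, against 89% with no shift. Those rank figures assume continuous differences without ties, which a 0 to 10 rating may not give.

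**5. Less balanced sequences, *p* = 0.5.** If 38 are allocated 19/19 and five are lost at random (both assumed), the hypergeometric probabilities are 66% for 17/16, 29% for 18/15 and 5% for 19/14.

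| Split | Bias | Paired t | With period term |
|---|---|---|---|
| 18/15 | 0.5 × 3/33 = 0.05 | 82% / 91% | 90% |
| 19/14 | 0.5 × 5/33 = 0.08 | 78% / 93% | 89% |

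Averaged over these splits, paired-test power is 90.1%, 88.9%, 86.6% and 82.8% at *p* = 0, 0.3, 0.5 and 0.7.

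**6. Price of the period term when there is no shift.** Power goes from 90.1% to 90.0% at 17/16, 89.8% at 18/15 and 89.4% at 19/14.

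**The case against.** The strongest reply is that the loss rests on a number that the documents do not contain. A shift of 0.5 is 71% of the lens effect being sought (0.5 / 0.7). Section 8.1 requires that each subject "Is an adapted soft contact lens wearer", so insertion and removal are practised skills, and handling is rated after two weeks and one month on each lens, which gives early practice effects time to fade. At a shift of 0.3 the average loss is only about one percentage point. This stands, and it limits how much weight the point can bear.

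Second, if 1.2 came from an earlier cross-over with randomised order, it may already contain period variance, and then there is no shortfall against 90%. With a total variance of 1.44 that includes *p* = 0.5, the residual SD is √(1.44 − 0.25) = 1.09. Paired-test power is then 91% / 93% at 17/16, against 95% with a period term. This also stands: on that reading the term adds power instead of restoring it. It still helps.

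Third, the paired test is not invalid. At *p* = 0.5 its type I error stays below 5% at 17/16, 18/15 and 19/14, and reaches only about 5.7% at a 20/13 split. This is correct.

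Fourth, the allocation scheme cannot be seen, because only the heading of Appendix 3 is shown. The imbalance figures are therefore conditional.

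Fifth, an analysis of variance could carry a period factor. But Section 10.1 does not say that it does, and the first-named method is the paired t-test.

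**Conclusion.** The concern holds as a modest, avoidable loss of precision. It is certain that no period term is specified for a two-period cross-over; the size of any shift is unknown. On the assumptions stated, a 0.5-point shift takes planned power from 90% to about 87%, and 0.3 takes it to about 89%. With near-equal sequences the bias is at most 0.02 points for shifts up to 0.7 (0.7 / 33 = 0.021), and false positives do not rise. Bias becomes noticeable only if the sequences finish clearly unequal. The case for changing the plan is that the trade is one-sided: about 0.1 percentage point lost at 17/16 if there is no shift, about three recovered if the shift is 0.5, and the imbalance bias removed in either case.

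**What to change.** In Section 10.1, replace the general statement for the primary outcome with wording such as: *The primary comparison of handling ratings uses a linear mixed model with fixed effects for lens and period and a random subject effect. The lens difference is reported with its 95% CI, together with the number of completers in each sequence.*

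For complete pairs the equivalent is a two-sample t-test between sequences on the period differences (period 1 minus period 2), with the estimate and its CI halved. A two-sample test between sequences on the lens differences must not be used in its place, because it tests the period effect. If a rank method is needed, use the rank-sum test between sequences on the same period differences. Keep the paired t-test or signed-rank test as a sensitivity analysis.

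The change needs one or two sentences and no extra subjects, visits or data, because the randomised sequence is already known. It uses one degree of freedom, and with no shift the power cost is 0.1 percentage point at 17/16, rising to 0.7 at 19/14. A period term does not remove carry-over.
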